9.6 Efficacy Subgroup Analyses

To evaluate the consistency of the efficacy over demographic and other Baseline characteristics, the primary efficacy endpoint will be analyzed in the following subgroups:

- Age group (≤ 50 and > 50)
- Age group (≥ 18 - < 28 , ≥ 28 - < 40 and ≥ 40)
- Sex (male, female)
- BMI (normal: < 25 , overweight: ≥ 25 - < 30 , obese: ≥ 30)
- Race (White, Asian, Black, and Other)
- Weight ($<$ median, \geq median)

- Baseline disease severity (T-VASI < 15 and \geq 15)
- Baseline disease severity (T-VASI \leq 10 and > 10),
- Status of active vitiligo (Yes/No)
- Baseline F-VASI (< median, \geq median)
- Fitzpatrick skin types (\leq II, III, > III)
- Duration of vitiligo since diagnosis (< median, \geq median)
- Prior topical therapy (with and without)
- Prior phototherapy (with and without)

'BMI \geq 30' or 'BMI \geq 25 - < 30' subgroups will be combined when either of the subgroups have fewer than 10% subjects. Any Race subgroups with fewer than 10% subjects will be combined with 'Other' subgroup for analyses.

10.0 Safety Analyses

10.1 General Considerations

Safety data will be summarized for each safety population.

10.2 Adverse Events

Adverse events (AEs) will be summarized and presented using primary MedDRA System Organ Classes (SOCs) and preferred terms (PTs) according to the version of the MedDRA coding dictionary used for the study at the time of database lock. The actual version of the MedDRA coding dictionary used will be noted in the AE tables and in the clinical study report. Specific adverse events will be counted once for each subject for calculating percentages, unless stated otherwise. In addition, if the same adverse event occurs multiple times within a subject, the highest severity and level of relationship to investigational product will be reported.

10.2.1 Treatment-Emergent Adverse Events

For Period 1, treatment-emergent adverse events (TEAEs) are defined as any adverse events that begin or worsen in severity after initiation of study drug through 30 days following the last dose of study drug in Period 1 or prior to first dose in Period 2, whichever is earlier. For Period 2, TEAEs are defined as any adverse events that begin or worsen in severity after initiation of study drug in Period 2 through 30 days following the last dose of study drug in Period 2. A TEAE during the administration of upadacitinib (i.e., among the ALL_UPA Population) is defined as any AE with an onset date on or after the first dose of upadacitinib and within 30 days after the last dose of upadacitinib. Events where the onset date is the same as the study drug start date are assumed to be treatment emergent.

All TEAEs will be summarized overall, as well as by primary MedDRA SOC and PT. The SOCs will be presented in alphabetical order, and the PTs will be presented in alphabetical order within each SOC. For the Safety_1 and ALL_UPA Populations, the number and percentage of subjects experiencing TEAEs and the number of events per 100 patient-years of exposure will be summarized.

10.2.2 Adverse Event Overview

An overview of AEs will be presented consisting of the number and percentage of subjects experiencing at least one event for each of the following AE categories for the Safety_1 and ALL_UPA Populations:

- Any TEAE
- Any TEAE related to study drug according to the investigator
- Any severe TEAE (Grade 3 and above according to National Cancer Institute (NCI) Common Terminology Criteria for Adverse Events (CTCAE) version 5)
- Any serious TEAE (SAE)
- Any TEAE leading to discontinuation of study drug
- Any TEAE leading to death
- TEAEs of special interest

- All deaths
- Deaths occurring \leq 30 days after last dose of study drug
- Deaths occurring $>$ 30 days after last dose of study drug.

The overview of number of TEAEs/deaths per 100 patient-years of exposure will also be provided for the above categories for the Safety_1 and ALL_UPA Populations.

TEAEs per 100 patient-years of exposure are defined as the number of TEAEs divided by the total exposure in 100 patient-years. The exposure-adjusted TEAE rate per 100 patient-years is calculated as:

$$100 \times \frac{\text{Number of TEAEs}}{\text{Total Patient Years}}$$

where total patient years is defined as the sum of the study drug duration (defined in Section 6.0) +1 day (not to exceed the start of subsequent period) of all subjects normalized by 365.25, and rounded to 1 decimal place.

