Key Eligibility Criteria:	
Eligible subjects will be adult females and males ≥ 18 to 65 years of age at Screening with a clinical diagnosis of NSV and no segmental or localized vitiligo, with all of the following at Screening and Baseline Visits: ≥ 0.5 F-VASI and ≥ 5 total Vitiligo Area Scoring Index (T-VASI). Subjects with other skin conditions that would interfere with evaluation of vitiligo, subjects with uncontrolled thyroid disease, and subjects with > 33% leukotrichia on the face or > 33% leukotrichia on the body (including face) are not eligible to enroll in this study.
 
Eligible subjects must not have previously been treated with any topical or systemic JAK inhibitor. Also, subjects must not have been previously treated with any permanent skin bleaching agents to treat vitiligo. Subjects must not have been treated with any systemic vitiligo therapy (e.g., methotrexate, mycophenolate mofetil, corticosteroids), supplemental vitiligo therapy (antioxidants/vitamins/herbal medicine/traditional Chinese medicine), and/or topical vitiligo therapy including permanent or temporary tattoos within a minimum of 30 days prior to the first dose of study drug (Note: Camouflage and makeup may be used). Eligible subjects must not have been treated with any phototherapy, including excimer (or other forms of laser therapy), within a minimum of 12 weeks prior to the first dose of study drug. Subjects who have had prior exposure to immunomodulatory

	
biologic therapy, for any indications, must have discontinued the biologic therapy prior to the first dose of study drug. Recommended washout periods for biologic therapies include <math>\geq 4</math> weeks for etanercept; <math>\geq 8</math> weeks for adalimumab, infliximab, certolizumab, golimumab, abatacept, tocilizumab, and ixekizumab; <math>\geq 16</math> weeks for secukinumab; and <math>\geq 12</math> weeks for ustekinumab. For biologic therapies not specified, therapies must be discontinued at least 5 times the mean terminal elimination half-life of a drug or 3 months prior to Baseline, whichever is longer.

Study Drug and Duration of Treatment:	
Upadacitinib 6 mg QD extended-release, film-coated tablets for oral administration, 52 weeks in duration.  Upadacitinib 11 mg or 22 mg QD extended-release, film-coated tablets for oral administration, 28 or 52 weeks in duration.  Placebo for upadacitinib QD film-coated tablets for oral administration, 24 weeks in duration.

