2.4 Sample Size Determination

Assuming a Week 24 percent change from Baseline in F-VASI of 0% in the placebo arm, a conservative estimate based on a prior study in vitiligo,¹ the planned total sample size of 160 subjects (40 subjects in each upadacitinib group, 40 subjects in total in the placebo groups) will provide more than 90% power to detect the treatment difference of 40% reduction (assuming a standard deviation of 54.8%) in at least 1 upadacitinib group versus placebo using a 2-sided significance level of 0.1 based on the two-sample t-test.

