6.0 Study Drug Duration and Compliance

For Safety_1/Safety_2 Population, duration of treatment will be summarized for each treatment group in Period 1 and Period 2. For ALL_UPA Population, duration of treatment will be summarized overall and for each upadacitinib dose group. Duration of treatment is defined as follows:

Period 1:

For subjects who did not continue into Period 2:

- Date of last dose of study drug in Period 1 – Date of first dose of study drug in Period 1 + 1.

For subjects who continued into Period 2:

- Minimum of (Date of first dose of study drug in Period 2 – Date of first dose of study drug in Period 1, Date of last dose of study drug in Period 1 – Date of first dose of study drug in Period 1 + 1.)

Period 2:

For subjects who continued into Period 2:

- Date of last dose of study drug in Period 2 – Date of first dose of study drug in Period 2 + 1.

ALL_UPA:

Study drug duration during the administration of study drug in ALL_UPA Population is defined as:

- Date of last dose of upadacitinib – Date of first dose of upadacitinib + 1.

Duration of treatment will be summarized using the number of subjects treated, mean, standard deviation, median, minimum and maximum. In addition, the number and percentage of subjects in each treatment duration interval (≥ 4 weeks, ≥ 12 weeks, ≥ 24 weeks, ≥ 36 weeks, ≥ 48 weeks) will be summarized for ALL_UPA Population.

Treatment compliance for Period 1 and 2 will be summarized by treatment groups for Safety Populations (Safety_1 and Safety_2). For ALL_UPA Population, treatment compliance will be summarized overall and for each upadacitinib dose group. Treatment compliance is defined as the number of tablets actually taken divided by the number of tablets that should have been taken. For subjects who prematurely discontinued the study drug, the planned tablets will only be counted prior to that scheduled visit of discontinuation. Percent compliance will be summarized.

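### TEAE rates count events for 30 days after the last dose but add only one day of person-time, so long-term rates may be up to about 9% too high

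*SAP*

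**What the plan says.** **Events counted.** SAP 10.2.1 runs the Period 1 window "through 30 days following the last dose of study drug in Period 1 or prior to first dose in Period 2, whichever is earlier". For ALL_UPA it counts "any AE with an onset date on or after the first dose of upadacitinib and within 30 days after the last dose of upadacitinib".

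**Person-time.** SAP 10.2.2 sets the denominator in these terms: "where total patient years is defined as the sum of the study drug duration (defined in Section 6.0) +1 day", continuing "not to exceed the start of subsequent period) of all subjects normalized by 365.25". For ALL_UPA, SAP 6.0 defines duration as "Date of last dose of upadacitinib – Date of first dose of upadacitinib + 1". That count already includes the last dosing day, and SAP 10.2.2 then adds one further day.

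**Where it is used.** SAP 10.2.1 to 10.2.5 give rates per 100 patient-years for Safety_1 and ALL_UPA, including serious events, discontinuations and events of special interest. No such rate is specified for Safety_2. The overview in SAP 10.2.2 also applies the rate to all deaths and to deaths more than 30 days after the last dose.

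Neither document gives a reason for using different windows.

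**The concern.** A rate per patient-year is interpretable when every counted event falls in time that the denominator also counts. Here the windows agree at the Period 1/Period 2 boundary: events are cut at the first Period 2 dose and the added day may not pass the start of the next period. They separate only after a subject's final dose.

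The tail is genuine follow-up. Protocol 6.1 collects adverse events for at least 30 days after the drug is stopped, and Protocol 5.6 and Appendix D provide a 30-day follow-up contact. Events there will be found and counted.

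The relative effect grows as exposure shortens. It is therefore larger for placebo subjects who switch to 28 weeks of drug, and for subjects who stop early. These rates are the SAP's means of allowing for unequal exposure across dose groups, so an error that itself depends on exposure length works against their purpose.

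**Working it through.** The documents state no expected rate or patient-years, so there is no figure of theirs to reproduce.

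**Inputs**
- Planned exposure (Protocol 1): "Upadacitinib 6 mg QD extended-release, film-coated tablets for oral administration, 52 weeks in duration", so d = 364 days; "Upadacitinib 11 mg or 22 mg QD extended-release, film-coated tablets for oral administration, 28 or 52 weeks in duration", so d = 364, or 196 for placebo switchers.
- Group sizes (SAP 2.4): "40 subjects in each upadacitinib group, 40 subjects in total in the placebo groups". SAP 2.2 sends 20 placebo subjects to 22 mg and 20 to 11 mg.
- Assumption: r is the event rate in the 30-day tail relative to the on-drug rate. The range 0 to 1 is shown.

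**Formula.** With d days of drug duration, the event window has d + 30 days and the SAP denominator d + 1. The difference is 29 days.

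Overstatement = (d + 30r)/(d + 1) − 1. For a group, sum numerator and denominator over subjects first.

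**Single exposures, r = 1**
- 52 weeks: 394/365 = 1.079, or +7.9%.
- 28 weeks: 226/197 = 1.147, or +14.7%.

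**ALL_UPA, all subjects completing as planned, r = 1**

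| Group | SAP person-days | Event-window days | Overstatement |
|---|---|---|---|
| 6 mg | 40×365 = 14,600 (40.0 years) | 40×394 = 15,760 (43.1 years) | 7.9% |
| 11 mg, and likewise 22 mg | 14,600 + 20×197 = 18,540 (50.8 years) | 15,760 + 20×226 = 20,280 (55.5 years) | 9.4% |
| All doses | 51,680 (141.5 years) | 56,320 (154.2 years) | 9.0% |

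Between doses: 1.094/1.079 = 1.013, about 1%.

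**Sensitivity of the ALL_UPA figure**
- r = 0.5: (120×379 + 40×211)/51,680 = 53,920/51,680, or +4.3%.
- r = 0: 51,520/51,680, or −0.3%, so no overstatement.
- r = 1 with an assumed 10% to 30% stopping at mid-course: +9.4% to +10.6%.

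**Safety_1, r = 1.** Subjects who go on to Period 2 have essentially no tail and contribute 168 days to both sums. Let a fraction p leave at day m (both assumed):

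Ratio = [168(1 − p) + p(m + 30)] / [168(1 − p) + p(m + 1)].

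- p = 5%, m = 56: 163.9/162.45, or +0.9%.
- p = 10%, m = 70: 161.2/158.3, or +1.8%.
- p = 20%, m = 56: 151.6/145.8, or +4.0%.
- p = 30%, m = 70: 147.6/138.9, or +6.3%.

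**The case against.** **The measure is labelled as exposure.** The SAP calls it events per 100 patient-years of exposure and defines it openly, and subject counts and percentages, which need no person-time, stand beside it. That is a fair defence of transparency. It does not explain the windows. The denominator is elapsed time from first to last dose plus a day, so it includes dose interruptions and is not strictly days on drug. The SAP also aligns the two windows at the period boundary and leaves only the final tail open.

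**The size rests on an assumption.** This stands. Nothing in the documents says that the on-drug rate persists for 30 days off drug. A reader might infer that long-term rates are simply overstated by 8% to 9%. For planned exposure the supported statement is a range from nil to about 9%.

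**Large percentages for early leavers.** A reader might infer that rates for subjects who leave early are inflated by up to 50%. The documents do not support this. The 50% is the single-subject value for leaving at about Week 8 (day 57: 87/58). It is not a maximum: leaving at day 28 gives 58/29, or +100%. More to the point, no rate for early leavers is planned, because the SAP pools them within treatment groups.

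**Biased comparisons.** A reader might also infer a material bias between arms. Between doses it is about 1%. In Safety_1, the only placebo-controlled set, even 10% dropout in one arm against 30% in another would shift the rate ratio by about 4% (1.063/1.018), and no figure in the documents suggests such a difference. With 40 to 60 subjects per dose group, shifts of this size are unlikely to change a safety conclusion.

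**Conclusion.** The mismatch is explicit in the SAP and holds as a minor point. Final ALL_UPA rates under planned exposure could be up to about 9% too high, the upper end requiring an unchanged event rate after the last dose. Safety_1 is affected by low single digits, about 1% to 6% at that same rate, under assumed dropout.

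Two qualifications apply:
- At the Week 24 analysis, subjects still on drug have no tail yet, so the ALL_UPA effect is smaller then than at the final analysis. The same definition carries a different inflation at the two looks.
- For deaths the mismatch is wider. Deaths more than 30 days after the last dose fall wholly outside the person-time by which they would be divided.

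**What to change.** In SAP 10.2.2:
1. For TEAE rates, define person-time from the first dose to the earliest of last dose + 30 days, the day before the first dose of the next period, last contact, and data cutoff.
2. Show the present drug-duration rate beside it.
3. For the all-deaths rate, use person-time to the end of follow-up. Report deaths more than 30 days after the last dose as counts, or on person-time accrued after the 30-day window.

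This needs one derived variable for the TEAE rates, a follow-up-time denominator for deaths, and a few lines of SAP text. It needs no new data or visits.

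There are two costs. The new rates are not directly comparable with rates built on the present definition. If risk falls off drug, the added days also dilute the rate: a 52-week subject with no tail events would show 365/394 of the present rate, about 7% lower. Showing both rates deals with each.

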10.2.3 Treatment-Emergent Adverse Events by SOC and/or PT

Treatment-emergent adverse events will be summarized by SOC and PT; by maximum relationship to study drug as assessed by the investigator (e.g., reasonable possibility or no reasonable possibility) and SOC and PT; by maximum toxicity and SOC and PT; by relationship to COVID-19 and SOC and PT; by $\geq 5\%$ subjects in any treatment group by SOC and PT. The number and percentage of subjects experiencing TEAEs will be provided for these summaries in the Safety_1 and ALL_UPA Populations. Number of TEAEs per 100 patient-years of exposure will be summarized by SOC and PT for the Safety 1 and All_UPA Populations. Specific adverse events will be counted once for each subject for calculating percentages, unless stated otherwise. In addition, if the same adverse event occurs multiple times within a subject, the highest toxicity and level of relationship to investigational product will be reported.

In addition, treatment-emergent adverse events will be summarized by PT and sorted by decreasing frequency for the total active treatment group.

10.2.4 SAEs (Including Deaths) and TEAE Leading to Study Drug Discontinuation

SAEs (including deaths) and TEAEs leading to study drug discontinuation will be summarized by SOC and PT and in listing format. The number and percentage of subjects experiencing SAEs and TEAE leading to study drug discontinuation as well as the number of events per 100 patient-years of exposure will be summarized for the Safety_1 and ALL_UPA Populations.

10.2.5 Adverse Events of Special Interest

Treatment emergent Adverse events of special interest (AESI) will be summarized by SOC and PT and will be based on standardized or company MedDRA queries (SMQs or CMQs) or based on adjudication results. The number and percentage of subjects experiencing treatment emergent AESIs and the number of events per 100 patient-years of exposure of the AESI overview table will be summarized for the Safety_1 and ALL_UPA Populations. For ALL_UPA, number of events per 100 patient-years of exposure of the AESI by SOC and PT will be summarized.

Adverse events of special interest are categorized as follows:

- Serious infections
- Opportunistic infection excluding tuberculosis and herpes zoster
- Possible malignancy
- Malignancy
- Non-melanoma skin cancer (NMSC)
- Malignancy excluding NMSC
- Lymphoma
- Hepatic disorder
- Adjudicated gastrointestinal perforation

- Anemia
- Neutropenia
- Lymphopenia
- Herpes zoster
- Renal dysfunction
- Active tuberculosis
- Adjudicated MACE
- Adjudicated VTE

Detailed information about the search criteria is provided in [Appendix B](#).

Tabular listings of adverse events of special interest will be provided.

10.3 Analysis of Laboratory Data

Data collected from central and local laboratories, including additional laboratory testing due to an SAE, will be used in all analyses, except for Baseline where SAE-related laboratory assessments on or before the first dose of study drug will be excluded. The clinical laboratory tests defined in the protocol operations manual (e.g., hematology and clinical chemistry) will be summarized.

Raw values and change from Baseline (percent change if applicable) to each applicable post-baseline visit will be summarized for selected laboratory variables in the Safety_1 and Safety_2 Populations. The following descriptive statistics will be presented by treatment groups: number of observations, Baseline mean (Standard deviation, SD), visit mean (SD), medium, change from Baseline mean (SD), standard error, and the 95% confidence interval of the mean change from Baseline.

Percent change from Baseline in LDL-C, HDL-C, total cholesterol and ratio of LDL-C to HDL-C will also be summarized similarly in the Safety_1 and Safety_2 Populations.

For the Safety_1 and ALL_UPA Populations:

A shift table from baseline to the worse post-baseline value (based on NCI CTC criteria) during treatment will be created. A similar shift table will be provided to summarize shifts from baseline to the final post-baseline value. The number and percentage of subjects will be summarized.

Laboratory abnormalities will be evaluated based on Potentially Clinically Important (PCI) criteria ([Appendix C](#)). For each laboratory PCI criterion, the number and percentage of subjects who have a laboratory value meeting the criteria will be summarized. Listings will be provided to summarize subject-level laboratory data for subjects meeting PCI criteria.

For the purpose of assessing for potential Hy's law cases, the frequencies and percentages of subjects with post-baseline liver specific function test values that meet PCI criteria ([Appendix C](#)) of potential clinical interest should be presented.

10.4 Analysis of Vital Signs

Vital sign measurements of systolic and diastolic blood pressure, heart rate, respiratory rate, and body temperature will be summarized.

Each vital sign variable will be summarized for all time points (starting with Baseline) with the number of non-missing observations, mean and standard deviation, median, minimum and maximum. Change from Baseline to each applicable post-baseline visit will be summarized for each vital sign variable, with the number of observations, Baseline mean, and visit mean. Mean, standard error, and 95% confidence interval will be presented for the change from Baseline within each treatment group in Safety_1 and Safety_2 Populations.

Vital sign variables will be evaluated based on PCI criteria ([Appendix C](#)) for the Safety_1 and ALL_UPA Populations. For each vital sign PCI criterion, the number and percentage of subjects who have a vital sign value meeting the criteria will be summarized. Listings

will be provided to summarize subject-level vital sign data for subjects meeting PCI criteria.

10.5 Safety Subgroup Analyses

Not applicable.

10.6 Other Safety Analyses

A post-Baseline treatment ECG listing will be provided.

11.0 Other Analyses

Not applicable.

12.0 Interim Analyses

No formal interim analysis of efficacy is planned for this study. Routine safety reviews will be performed by an external DMC.

12.1 Data Monitoring Committee

An external data monitoring committee (DMC) composed of persons independent of AbbVie and with relevant expertise in their field will periodically review unblinded safety data from the ongoing study. The primary responsibility of the DMC will be to protect the safety of the subjects participating in this study.

A separate DMC charter describes the roles and responsibilities of the DMC members, frequency of data reviews, relevant data to be assessed, and general operations.

Since there are no efficacy analyses for early stopping, no alpha adjustment is needed.

